**Correlation Between Monocyte / Lymphocyte Ratio and Risk of Death and
Cardiovascular Events in Patients Receiving Peritoneal Dialysis: a Multicenter
Prospective Cohort Study**

ClinicalTrials.gov ID: NCT04238338

01/07/2020

Background

The epidemiological survey of chronic kidney disease in China shows that the current incidence of chronic kidney disease (CKD) in China is about 10.8%, with about 119 million patients. About 2% of patients will enter the stage of end-stage renal disease (ESRD) and require dialysis or kidney transplantation to support life. Currently the main renal replacement therapy is: hemodialysis (HD) or peritoneal dialysis (PD). Among them, PD patients are increasing year by year. As of 2016, more than 900,000 people in Asia are undergoing maintenance dialysis (218 cases per million population). Statistics from the CNRDS system show that as of the end of 2017, the number of PD patients in China has reached 86264. Compared with HD, PD is easy to operate, better preserves residual renal function, has early survival advantages, and is more cost-effective. In spite of this, the prognosis of PD patients is still unsatisfactory. At present, the main causes of death in PD patients are cardiovascular disease, peritoneal dialysis-related peritonitis, gastrointestinal bleeding, and tumors. Among them, cardiovascular disease (CVD) is the most important, accounting for about 50% of the deaths of PD patients. Among all CVD events, coronary heart disease, heart failure, and stroke are the most common.

CVD risk factors for dialysis patients can be divided into traditional and non-traditional categories. Traditional Framingham risk factors can only explain some of the CVD risks of PD patients. Non-traditional risk factors, especially persistent inflammatory states, are essential in the pathogenesis of CVD such as atherosclerosis and vascular calcification, and lead to protein energy expenditure and premature death outcomes in patients with CKD. The causes of chronic inflammation in patients with peritoneal dialysis are mainly divided into two aspects. Dialysis-related factors include: catheter-related infections, continuous exposure to biologically incompatible PD solutions, peritonitis, increased adipose tissue, and adipose factor balance disorders; associated with low GFR Factors include decreased clearance of pro-inflammatory factors, accumulation of uremic toxins, endotoxin exposure, oxidative stress, increased volume load, oral or other organ infections, and susceptibility to infections. The causes of inflammation in peritoneal dialysis are interconnected, leading to a persistent state of inflammation that ultimately increases the risk of cardiovascular events. Therefore, it is important to screen for markers that predict the risk of CVD in dialysis patients.

At present, various inflammatory mediators, such as c-reactive protein (CRP), interleukins (IL) and tumor necrosis factor (TNF), have been studied and proven to independently predict the risk of CVD in dialysis patients. CRP can induce the expression of adhesion molecules in endothelial cells, increase the adhesion of vascular endothelial cells and monocytes; promote the formation of foam cells and atherosclerosis; aggravate vascular endothelial dysfunction; TNF- α can increase the expression and activity of alkaline phosphatase, enhance Isolated

vascular wall calcification; aggravates vascular endothelial dysfunction; promotes left ventricular remodeling and aggravates left ventricular dysfunction. IL-6 can stimulate macrophages to secrete monocyte chemoattractant protein 1, induce endothelial cell adhesion molecule expression; stimulate vascular smooth muscle cell proliferation and migration; aggravate vascular endothelial dysfunction; and induce cardiac hypertrophy. Although the mechanisms are different, they all increase the risk of CVD death in dialysis patients by aggravating vascular endothelial dysfunction, promoting ventricular remodeling and inducing myocardial hypertrophy. However, such markers are expensive and their detection is not easy to limit their clinical application. This prompted researchers to devote themselves to mining new markers of inflammation.

In recent years, experts and scholars have become interested in blood cell parameters. Previous studies have shown that white blood cells and their subgroups (neutrophils, lymphocytes, monocytes, Neutrophil / lymphocyte ratio (NLR), monocyte /lymphocyte ratio (MLR), platelet / lymphocyte ratio (PLR) and other indicators have important predictive value for all causes and prognosis of cardiovascular disease in dialysis population. They have the advantages of low cost and easy detection. Among them, MLR has been proven to be an independent predictor of death in cardiovascular diseases such as coronary heart disease and heart failure. Previous research found. Monocytes play a key role in the occurrence and development of atherosclerosis. After the initial injury, endothelial cells are activated and promote monocytes to roll, attach and migrate under the endothelium. Monocytes that migrate to the subendothelial can differentiate into dendritic cells, which are key participants in activating adaptive immunity, or differentiate into macrophages, which secrete pro-inflammatory cytokines, thereby recruiting more immune cells and Promote inflammation. Macrophage phagocytosis of lipoprotein particles can lead to the formation of fatty streaks, the earliest ultrastructural changes in the formation of atherosclerosis. The migration of smooth muscle cells from the medial membrane to the intimal membrane further promotes the atherogenic process. Monocyte-derived cells transform this early lesion into advanced atherosclerotic plaques, which contain lipid-rich and macrophage-rich necrotic cores that eventually cause the plaque to rupture. In addition, previous studies have shown that physiological stress can lead to a significant increase in systemic cortisol production, which has led to a shift in leukocyte differentiation toward a decrease in lymphocytes and an increase in the percentage of granulocytes. Measuring lymphocyte counts can reflect stress levels. In patients with coronary heart disease, studies have shown that a decrease in lymphocyte count is an independent predictor of prognosis in patients with coronary heart disease; there is a phenomenon of lymphocyte apoptosis on the endothelium of atherosclerotic injured blood vessels. Therefore, low lymphocytes can reflect the occurrence and development of atherosclerotic diseases. In patients with end-stage renal disease, there will be changes in the number of immune cells such as increased

monocytes and decreased lymphocytes. First, the decline in renal function causes retention of uremic toxins and cytokines, which leads to increased proinflammatory cytokines and oxidative stress. It further stimulates the proliferation of monocytes, and at the same time down-regulates immunity, resulting in a decrease in the number and function of lymphocytes, which in turn promotes inflammation and oxidative stress, and continues a vicious cycle. MLR can integrate pro-inflammatory and anti-inflammatory effects, and simultaneously reflect inflammation and immune deficiency. It may be an important marker of inflammation in patients with end-stage renal disease. In 2017, Xiang F et al. For the first time found in a prospective cohort study of 355 hemodialysis patients that high MLR levels were independent predictors of all-cause and CVD mortality in hemodialysis patients, and exceeded the predictive value of NLR. However, there are no reports about MLR and prognosis in patients with peritoneal dialysis at home and abroad. Our previous retrospective analysis showed that the all-cause and cardiovascular disease survival rates of patients in the low MLR group were significantly higher than those in the high MLR group; high MLR levels were associated with all-cause and increased risk of cardiovascular death in patients with peritoneal dialysis. However, because single-center retrospective studies cannot determine causality, there may be problems such as selection bias. Therefore, a multicenter, prospective, large-sample study is needed to further explore the correlation between MLR and the prognosis of PD patients.

Summary

Title	Correlation Between Monocyte / Lymphocyte Ratio and Risk of Death and Cardiovascular Events in Patients Receiving Peritoneal Dialysis: a Multicenter Prospective Cohort Study.
Sponsor	Department of Nephrology of Zhujiang Hospital, Southern Medical University
Study official	[name]
Research purposes	Main research purpose: To explore the correlation between MLR and risk of death and cardiovascular events in patients receiving peritoneal dialysis. Secondary research purpose: To explore the correlation between MLR and peritoneal dialysis-associated peritonitis in patients with peritoneal dialysis.
Research hypothesis	The level of MLR is related to the prognosis of patients with peritoneal dialysis. High levels of MLR may increase the risk of death, cardiovascular events and dialysis-associated peritonitis in patients with peritoneal dialysis.
Study Model	prospective cohort study

Sample size	
This study is based on a balanced control design of two groups to test whether there is a significant difference in survival rates. All-cause mortality and cardiovascular mortality are Primary Outcome Measures. Divided into high MLR group and low MLR group according to the median of monocyte / lymphocyte ratio (MLR). The previous research results show that the one-year survival rate of patients in the high MLR group was 86.6%, and the survival rate of patients in the low MLR group was 97%. Taking 0.05 as the statistical significance level on both sides, setting the test efficiency to 80%, adopting a 1: 1 balanced design, calculated by software PASS.11, it requires 84 cases in the high MLR group and 84 cases in the low MLR group. The one-year cardiovascular survival rate of patients in the high MLR group is 90.7%, and the cardiovascular survival rate of patients in the low MLR group 98.6%, taking 0.05 as the statistical significance level on both sides, setting the test efficiency to 80%, adopting a 1: 1 balanced design, calculated by software PASS.11, 127 cases are required in the high MLR group and 127 cases are in the low MLR group. Further assuming that the maximum rate of lost follow-up in each group will not exceed 5%, the final sample size is determined as 133 cases in the high MLR group and 133 cases in the low MLR group, for a total of 266 cases.

-------------	-----------------------------------------------------------------------------------------------------------------------------------------------------------------------------------------------------------------------------------------------------------------------------------------------------------------------------------------------------------------------------------------------------------------------------------------------------------------------------------------------------------------------------------------------------------------------------------------------------------------------------------------------------------------------------------------------------------------------------------------------------------------------------------------------------------------------------------------------------------------------------------------------------------------------------------------------------------------------------------------------------------------------------------------------------------------------------------------------------------------------------------------------------------------------------------------------------------------------------------------------------------------------------------------------------------------------------------------------------------------------------------------------------------------------------------------

Eligibility	
Study Population: Patients who underwent continuous ambulatory peritoneal dialysis in the Department of Nephrology of Zhujiang Hospital of Southern Medical University, Guangzhou First People's Hospital, and Jiangmen Central Hospital, and voluntarily signed informed consent to join the study.
 
Inclusion Criteria:
 
• Patients who underwent continuous ambulatory peritoneal dialysis for at least 3 months. 
Exclusion Criteria:
 
• Age <18 years, with acute or chronic infections such as lung infection, peritoneal dialysis-related peritonitis, urinary system infection, etc.• With history of malignant tumor or blood disease.• With rheumatic immune diseases, such as systemic lupus erythematosus, vasculitis, sjögren's syndrome, etc.• Used immunosuppressants, such as glucocorticoids, calcineurin inhibitors, etc.• Women during pregnancy.
-------------	------------------------------------------------------------------------------------------------------------------------------------------------------------------------------------------------------------------------------------------------------------------------------------------------------------------------------------------------------------------------------------------------------------------------------------------------------------------------------------------------------------------------------------------------------------------------------------------------------------------------------------------------------------------------------------------------------------------------------------------------------------------------------------------------------------------------------------------------------------------------------------------------------------------------------------------------------------------------------------------------------------------------------

Follow up	
The follow-up period was from the beginning of the study to the first outcome event (death or cardiovascular event, peritoneal dialysis-associated peritonitis). For patients who did not have an outcome event or survived, the follow-up period is 1 year. The lymphocyte / monocyte ratio should be tested every 3 months after the start of the study, and the final value is the average.

Exposure factor	Monocyte / lymphocyte ratio (MLR)
Outcome Measures	
Primary Outcome Measure:
 
 • All-cause mortality • Cardiovascular mortality 
Secondary Outcome Measure:
 
 • The Incidence of cardiovascular events (including acute heart failure, angina, acute myocardial infarction, arrhythmias requiring treatment, transient ischemic attack (TIA), cerebral infarction or cerebral hemorrhage, peripheral vascular disease) • The Incidence of peritoneal dialysis-associated peritonitis

Data Sources	
Use a combination of electronic medical record system, test report system, national peritoneal dialysis information registration system, cardiovascular event registration form to collect patient clinical and demographic data, laboratory data, and survival outcomes. For out-of-hospital events, relevant information is obtained by telephone follow-up.
 
Clinical and demographic data : age, gender, body mass index (BMI), dialysis time, smoking history, family history, medication history, medication status, primary kidney disease and complications
 
Laboratory data: Peritoneal balance test (PET), dialysis adequacy assessment (KT/v), c-reactive protein (CRP), erythrocyte sedimentation rate (ESR), procalcitonin (PCT), interleukin 6 (IL-6), whole blood count and classification of leukocyte count, calcium, phosphorus, intact parathyroid hormone (IPTH), serum iron, ferritin, transferrin, transferrin saturation, urea nitrogen, serum creatinine, uric acid, urinary protein ,estimated glomerular filtration rate (eGFR), blood glucose, total cholesterol, triglyceride, high-density lipoprotein, low-density lipoprotein, albumin (ALB), N-terminal pro-brain natriuretic peptide, pulse pressure (PP), blood pressure,(BP) , left ventricular mass index (LVMI), ejection fraction (EF), carotid artery intima-media thickness (IMT).

--------------	------------------------------------------------------------------------------------------------------------------------------------------------------------------------------------------------------------------------------------------------------------------------------------------------------------------------------------------------------------------------------------------------------------------------------------------------------------------------------------------------------------------------------------------------------------------------------------------------------------------------------------------------------------------------------------------------------------------------------------------------------------------------------------------------------------------------------------------------------------------------------------------------------------------------------------------------------------------------------------------------------------------------------------------------------------------------------------------------------------------------------------------------------------------------------------------------------------------------------------------------------------------------------------------------------------------------------------------------------------------------------------------------


Statistical plan
	
Statistical hypothesis: test hypothesis H0: $\lambda 1 = \lambda 2$, that is, there is no difference in mortality and the Incidence of cardiovascular events between the high MLR group and the low MLR group.
 
Alternative hypothesis H1: $\lambda 1 \neq \lambda 2$, there is a statistical difference in mortality and the Incidence of cardiovascular events between the high MLR group and the low MLR group.
 
Main statistical analysis methods: Spss23.0 software was used for data statistical analysis. The continuity variables were tested for normality first. The continuous variables of normal distribution are represented by 'x \pm s'; the continuous variables of skew distribution are represented by median m; the data of classification or counting type are displayed by percentage. Two independent samples were used to compare the differences between groups in normal distribution measurement data, Mann Whitney U test was used to compare the differences between groups in non normal distribution measurement data, and chi square test was used to compare the differences between groups in classification or counting data. For missing values such as missing values and censored values, when the missing values are concentrated in a few variables and these variables are not the main variables for analysis, deletion can be considered, or the mean substitution method can be used to find alternative values for the missing values. The correlation between MLR and other indexes was analyzed by Spearman correlation and linear regression. Kaplan Meier curve was drawn to estimate the survival rate and cardiovascular disease incidence rate, and log rank test was used to check the difference. Single factor and multiple factor Cox regression models were used to explore the independent risk factors of death and cardiovascular disease in peritoneal dialysis patients, and to evaluate the correlation between MLR level and clinical all-cause and cardiovascular disease-related survival outcomes in peritoneal dialysis patients. Using HR risk ratio (95% CI confidence interval) to show the results, bilateral

-------------------------	-------------------------------------------------------------------------------------------------------------------------------------------------------------------------------------------------------------------------------------------------------------------------------------------------------------------------------------------------------------------------------------------------------------------------------------------------------------------------------------------------------------------------------------------------------------------------------------------------------------------------------------------------------------------------------------------------------------------------------------------------------------------------------------------------------------------------------------------------------------------------------------------------------------------------------------------------------------------------------------------------------------------------------------------------------------------------------------------------------------------------------------------------------------------------------------------------------------------------------------------------------------------------------------------------------------------------------------------------------------------------------------------------------------------------------------------------------------------------------------------------------------------------------------------------------------------------------------------------------------------------------------------------------------------------------------------------------------------------------------------------------------------------------------------------------------------------------------------------------------------------------------------------------------------------------------------------------------------------------------------------------------------------------------------------------------------------------------------------------------------------------------------------------------------------------------------------------------------------------------------------------

	statistical standard p value < 0.05 has statistical significance.
--	-------------------------------------------------------------------

References

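### MLR is defined as an average of tests taken during follow-up, yet survival is counted from study start, so exposure uses information from after time zero

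*Combined protocol and SAP*

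**What the plan says.** All references are to the Summary table of the combined protocol and SAP.

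- **Follow up, time axis.** "The follow-up period was from the beginning of the study to the first outcome event", whether death, a cardiovascular event or peritonitis. "For patients who did not have an outcome event or survived, the follow-up period is 1 year".
- **Follow up, exposure value.** "The lymphocyte / monocyte ratio should be tested every 3 months after the start of the study, and the final value is the average". The ratio is written upside down here; the Exposure factor row and the title have monocytes over lymphocytes.
- **Sample size.** Patients are split at the median MLR. The row does not say which MLR value is split.
- **Statistical plan.** "Kaplan Meier curve was drawn to estimate the survival rate and cardiovascular disease incidence rate, and log rank test was used to check the difference". Univariable and multivariable Cox models follow. No enrolment value, landmark, lag or time-dependent covariate is mentioned.
- **Data Sources.** A blood count with differential is listed, without timing.
- **Missing data (Statistical plan).** Deletion or mean substitution is allowed "when the missing values are concentrated in a few variables and these variables are not the main variables for analysis".

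**The concern.** The study asks whether the level of MLR is associated with later death and cardiovascular events. That requires the exposure to be known when the clock starts. An average over follow-up is not known then, and three problems follow.

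1. **Reverse causation.** Readings taken while a patient is deteriorating enter the exposure. The Background section gives a mechanism: physiological stress lowers lymphocytes, and inflammation goes with more monocytes. The Eligibility row excludes infection at entry, but nothing screens later readings for intercurrent illness.
2. **Survival decides how many readings are averaged.** If MLR drifts over time in the whole cohort, early deaths and survivors are averaged over different calendar stretches, and an association can arise from that alone.
3. **Early deaths may have no exposure.** Tests are scheduled only after study start. If the first is at month 3, a patient who dies sooner has no MLR, and everyone who can be classified has survived 3 months by construction.

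Both primary outcomes, all-cause and cardiovascular mortality, rest on this exposure.

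**Working it through.** **Step 1. Reproduce the plan's sample size, which sets the event counts.** Inputs from the Sample size row: one-year cardiovascular survival 90.7% and 98.6%, two-sided 0.05, power 80%, 1:1.

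n per group = [1.960 × √(2 × 0.0535 × 0.9465) + 0.842 × √(0.093 × 0.907 + 0.014 × 0.986)]² / 0.079² = 126.2, rounded up to 127, as stated. Adding 5% gives 127 × 1.05 = 133.35, against the stated 133 (dividing by 0.95 gives 133.7). The total of 266 is used below. The all-cause calculation does not drive it.

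**Step 2. Expected deaths, and deaths before month 3** (constant hazard assumed).

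- All-cause: mean mortality (13.4% + 3.0%)/2 = 8.2%; 266 × 0.082 = 21.8 deaths. Before month 3: 266 × (1 − 0.918^0.25) = 5.6, or 26%.
- Cardiovascular: mean (9.3% + 1.4%)/2 = 5.35%; 266 × 0.0535 = 14.2 deaths. Before month 3: 266 × (1 − 0.9465^0.25) = 3.6.

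Applying the hazard separately in each group gives 5.7 and 3.7.

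**Step 3. Number of readings.** With tests at months 3, 6, 9 and 12, one-year survivors have 4. Deaths spread about evenly over the four quarters have 0, 1, 2 or 3 readings, on average 1.5. Adding a month-0 test makes these 5 and 2.5.

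**Step 4. Simulation with no true association.** Plan inputs: N = 266, 8.2% one-year mortality, 3-monthly tests, median split of the average, log-rank at two-sided 0.05. Assumptions not in the documents: exponential death times, log-normal MLR with log-SD 0.45, within-patient correlation 0.6, readings stopping at death, and the rises and trends shown. In (a) a month-0 value, unaffected by the rise, is included; in (b) the first test is at month 3. There were 4,000 runs per scenario. Entries are the apparent hazard ratio and the false-positive rate.

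| Assumed MLR behaviour | (a) month 0 included | (b) first test at month 3 |
|---|---|---|
| No rise, no trend | 0.96, 5% | 0.95, 5% |
| 1.25-fold rise, last 3 months | 1.22, 8% | 1.61, 15% |
| 1.5-fold rise, last 3 months | 1.54, 16% | 2.46, 41% |
| 2-fold rise, last 3 months | 2.20, 42% | 5.01, 82% |
| Same rises, last month only | 1.03 to 1.24, 5% to 8% | 1.11 to 1.51, 5% to 13% |
| Trend +20% per year, no rise | 0.76, 10% | 0.80, 8% |
| Trend −20% per year, no rise | 1.23, 7% | 1.15, 5% |

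For the 1.5-fold, 3-month rise, varying log-SD from 0.3 to 0.6 and correlation from 0.4 to 0.8 gives hazard ratios of 1.3 to 2.0 in (a) and 1.9 to 4.2 in (b).

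**Step 5. Alternatives under the same 3-month rises.**

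- Enrolment value alone: hazard ratio about 1.0 (5%) if it is unaffected by the rise; 1.2 to 1.6 (7% to 19%) if it is already raised in patients who die within 3 months. That information is at least available at time zero.
- Time-dependent MLR without a lag: 1.8, 2.5 and 3.6 (26%, 60% and 88%). Future information is gone, but reverse causation is not.
- Time-dependent MLR with a 3-month lag: 1.0 (5%), because the lag matches the assumed window.

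**The case against.** The strongest reply is that the plan never says the groups are formed from the average. The Sample size row does not name the value that is split, and an enrolment count may exist among the listed laboratory data. This stands as a caution: the link is an inference. But the average is the only MLR value the plan defines, so an analyst following the text would use it. If an enrolment split was intended, the plan still has to say so.

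The second reply is about size, and much of it stands. Only the death counts rest on plan figures. With no rise and no trend there is no inflation of false positives, and a one-month rise does little harm. The plan's rates imply hazard ratios of ln 0.866/ln 0.97 = 4.7 (all-cause) and ln 0.907/ln 0.986 = 6.9 (cardiovascular); in the Step 4 table only a doubling with the first test at month 3 exceeds the lower of these. An observed effect that large would be hard to attribute wholly to this bias.

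The simulation also lets readings continue to death, whereas the plan ends follow-up at the first event of any kind. If half of the deaths were preceded by an event that stopped readings at illness onset (an assumption), the three 3-month rises would give hazard ratios of about 1.06, 1.18 and 1.39 in (a) and 1.28, 1.61 and 2.31 in (b), with false positives of 6% to 11% and 8% to 31%. That is smaller but not gone. The plan does not say whether readings stop at a non-fatal event.

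The missing-data wording is ambiguous: mean substitution might be meant to extend to MLR. This would not help, since early deaths would then be given a cohort mean in place of a measurement.

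Finally, an enrolment value does not remove illness already present at entry. With a rise lasting 6 months it gave hazard ratios of 1.5, 1.9 and 2.6 (13%, 32% and 57% false positives). This is why lagged analyses belong in the fix.

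**Conclusion.** The concern holds, and the definition must be changed before the analysis. Relating an average of later readings to survival from study start is wrong as written; it is more than a missing detail. That conclusion needs no simulation, only the reading that the median split and Cox term use the one MLR value defined.

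The documents support the existence of the exposure to bias but not its size or direction. Under the plan's rates and a constant hazard, about a quarter of deaths have no MLR on the literal schedule. Beyond that, the distortion ranges from negligible (no rise, no trend) to severe (a sustained doubling before death), and an upward cohort trend would push the other way. Neither a positive nor a null result could therefore be attributed cleanly to the prognostic value of MLR. The inverted ratio in the Follow up row is an editorial slip, though applied literally it would swap the high and low groups.

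**What to change.** - In the Follow up row, schedule a blood count at enrolment and define the primary exposure as MLR from that count. Remove the average as the exposure definition.
- In the Sample size and Statistical plan rows, state that the median split and the main Cox term use the enrolment value alone.
- Keep the 3-monthly values for secondary analyses: a time-dependent Cox model in which each value counts only after it is drawn, with a lagged version (for example 3 months) as a sensitivity analysis, or a landmark analysis averaging only values before the landmark. Because the right lag is unknown, report more than one.
- State whether readings after a non-fatal event are used, and how a missing enrolment MLR is handled.
- Write the ratio as monocyte/lymphocyte throughout.

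The cost is wording plus one explicitly scheduled count. It has to be settled before enrolment, because a missed enrolment count cannot be recreated. The downside is that a single value is noisier than an average, which the secondary analyses only partly offset.
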